Over a period of six months, all consecutive consenting patients undergoing on pump coronary bypass grafting surgery requiring sternotomy will be enrolled. The patients will be randomized into two groups. The control group will receive standard of care sternal closure. The study group will receive standard of care sternal closure plus PRP applied to the sternum and the surrounding tissue at the time of closure. Participants and outcome assessors are blinded to group assignment, while surgeons performing the procedure are aware of the intervention. The patients will be followed up for a period of 30 days post-surgery. Wound healing, deep and superficial infection including mediastinitis, and readmissions within 30 days will be documented as primary outcomes. Secondary outcome will be the overall cost burden for the 30-days post-surgery period. Other outcomes will be ICU stay (days), blood transfusions more than 4 units and platelets transfusions more than 4 units.

Discussion

Wound dehiscence and infection in post cardiac surgery period are a significant source of morbidity and mortality. Treatment of these complications may cause prolonged hospitalization, prolonged antibiotic therapy, and revisions of operative procedures. In addition to burden on physical health, the complications associated with cardiac surgery can portend a high financial cost to the patient. The PRP has been shown to decrease the incidence of sternal wound complications following cardiac surgery and routine use of platelet rich plasma has been advocated for all patients undergoing sternotomy for cardiac surgical procedures.

Keywords

Sternal wound infection, Superficial sternal wound infection, Deep sternal wound infection, Surgical site infection, Delayed wound healing, Median sternotomy, Cardiac surgery, Postoperative wound complications, Hospital length of stay, Cost analysis, Platelet rich plasma, coronary artery bypass grafting, wound healing, CABG, readmission rate

INTRODUCTION

Median sternotomy in cardiac surgery is considered to be the gold standard incisional approach for the majority of cardiac operative procedures resulting in a low failure rate and excellent long-term outcomes [1].

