Postoperative complications cause significant morbidity in post cardiac surgery patients. The PRP has been proposed in clinical trials to reduce the frequency of complications in patients undergoing median sternotomy for cardiac operative procedures. The purpose of our study is to evaluate whether there is any beneficial effect of use of PRP in addition to standard care after on pump CABG, cardiac surgery.

Research Question

Does application of PRP after CABG, cardiac surgery reduce the frequency of sternal wound complications?

Objective

To compare the complication rates of application of PRP in addition to standard sternal wound closure versus standard sternal wound closure alone.

Population

All consecutive patients of age 45 to 72, undergoing CABG, cardiac surgery with median sternotomy will be included in the study.

Intervention

Application of 6 mL of autologous PRP to sternum and soft tissue during sternal closure.

Comparison

The control group will undergo midline sternotomy with a sternal saw blade. The sternum will be closed with a simple interrupted or figure of eight stainless steel wire. The wounds will be closed in a layered manner with absorbable suture and dressed with Steri-Strips, gauze and paper tape. The study group will additionally receive 6 mL of autologous PRP applied to sternum and soft tissue during sternal closure.

Outcome

(i) Primary Outcome;

Primary outcome will be measured as frequency of sternal wound complications in terms of delayed healing, superficial infection, deep infections, and readmission rate including mediastinitis in 30-days period post-surgery.

(ii) Secondary outcome;

Secondary outcome will be the overall cost burden for the 30-days post-surgery period.

(iii) Other outcomes;

Other outcomes will be ICU stay (days), blood transfusions more than 4 units and platelets transfusions more than 4 units within 30 days.

OPERATIONAL DEFINITIONS

1-Cardiac Surgery: Cardiac surgery, also called heart surgery, involves surgical operations performed on the heart to correct life-threatening conditions. The surgery can be either open-heart surgery or minimally invasive surgery depending on the condition to be corrected.

2-PRP: Platelet-rich plasma (PRP) is defined as a portion of the plasma fraction of autologous blood having a platelet concentration above baseline.

3-Study Outcome

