Study Outcome will be measured as frequency of sternal wound complications in terms of delayed healing, superficial infection, deep infections, and readmission rate including mediastinitis in 30-days period post-surgery. Secondary outcome will be the overall cost burden for the 30-days post-surgery period. Other outcomes will be ICU stay (days), blood transfusions more than 4 units and platelets transfusions more than 4 units within 30 days.

4- DSWI: DSWI diagnosis will be made, based on the guidelines of the CDC, in patients who developed one or more of the following: [1] positive culture of mediastinal tissue or fluid; [2] clinical evidence of mediastinitis during sternal reoperation; or [3] chest pain, sternal instability, purulent discharge from the mediastinum associated with a positive blood culture. DSWI presenting in the first 30 days after operation will be included in the study.

5- SWI: All the infections will be considered positive that will involve skin and subcutaneous tissue within the first 30 postoperative days, not reaching the sternum, requiring local surgical intervention with regular wound care, accompanied by antibiotic therapy and/or Vacuum Assisted Closure (VAC) therapy.

6- Delayed Healing: Healing is a complex biochemical process of tissue repair after it has been damaged. It has three stages which are inflammation, proliferation and remodelling. Delay in the specific time period or in the biochemical process is called delayed healing. Skin,

subcutaneous tissue or sternum which is unable to heal within two weeks of surgery will be considered delayed wound healing.

7- Readmission: It is defined as any hospital readmission within 30 days of discharge related to the index surgery.

8- ICU stay: Stay that refers to the duration, in days, spent in the intensive care unit, within 30 days postoperatively.

9- Blood transfusion: It is defined as the requirement of more than 4 units of packed red blood cells (PRBC) or platelets within 30 days postoperatively.

Hypothesis

Administration of platelet rich plasma during sternal wound closure reduces the frequency of complications in the 30-days post-surgery period.

MATERIAL AND METHODS

Study Design

Randomized control trial

Study Setting

The Department of Cardiac Surgery, Cardiac Center, Pakistan Institute of Medical Sciences (PIMS), Islamabad.

Duration

06 months after acceptance of synopsis

Sample selection;

Inclusion criteria

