tissue during sternal closure. Participants and outcome assessors will be blinded to group assignment, while surgeons performing the procedure will be aware of the intervention

Primary outcome will be measured as frequency of sternal wound complications in terms of delayed healing, superficial infection, deep infections, and readmission rate including mediastinitis in 30-days period post-surgery. Secondary outcome will be the overall cost burden for the 30-days post-surgery period. Other outcomes will be ICU stay (days), red cell concentrate (RCC) more than 4 units and platelets transfusions more than 4 units.

All the information will be entered on the predesigned Performa by the researcher himself to comply with the study protocol attached as **Annexure-I**.

Data Analysis

Quantitative variables (age, hospital stay, ICU stay, cost) will be summarized as mean \pm SD or median (IQR) and compared using t-test or Mann-Whitney U test. Categorical variables (superficial/deep wound infections, delayed healing, readmissions, transfusion requirements, residence (urban\rural), education status and socioeconomic background (low\middle) will be reported as counts and percentages and compared using chi-square or Fisher's exact test. A p-value <0.05 will be considered significant. Missing data will be handled using complete case analysis. All analyses will be performed using [SPSS/R].

Ethical Considerations

From ethical point of view:

- Those patients will be included in the study that will be willing to participate in the study.
- A written informed consent will be taken from the patients and they will be ensured that their confidentiality will not be breached.
- There will be no compromise on the standard care and treatment for study purposes.

References

- [1] Reser, Diana, et al. "Median sternotomy." *Multimedia manual of cardiothoracic surgery: MMCTS 2015* (2015).
- [2] Balachandran, Sulakshana, et al. "Risk factors for sternal complications after cardiac operations: a systematic review." *The Annals of thoracic surgery* 102.6 (2016): 2109-2117.
- [3] Patel, Amit N., et al. "Evaluation of autologous platelet rich plasma for cardiac surgery: outcome analysis of 2000 patients." *Journal of cardiothoracic surgery* 11.1 (2016): 1-6.
- [4] Heilmann, Claudia, et al. "Wound complications after median sternotomy: a single-centre study." *Journal of cardiothoracic surgery* 13.1 (2018): 1-6.

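### The protocol does not fix whether the primary outcome is one overall complication frequency or several separate outcomes, and no comparison is named as the deciding one

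*Protocol*

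**What the plan says.** The protocol describes the primary outcome in several places.

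- **Opening summary (methods paragraph):** "Wound healing, deep and superficial infection including mediastinitis, and readmissions within 30 days will be documented as primary outcomes". This is plural, item by item. Follow-up is given as "The patients will be followed up for a period of 30 days post-surgery".
- **Outcome section, item (i):** "Primary outcome will be measured as frequency of sternal wound complications in terms of delayed healing, superficial infection, deep infections, and readmission rate". This is singular, and its window is 30 days after surgery. The Data Collection Procedure repeats it.
- **Operational Definitions, item 3:** "Study Outcome will be measured as frequency of sternal wound complications in terms of delayed healing, superficial infection, deep infections, and readmission rate". The content is the same under a different label.
- **Operational Definitions, items 4 to 7:** deep infection, superficial infection, delayed healing and readmission are each defined. The overall frequency is not.
- **Readmission (item 7):** "It is defined as any hospital readmission within 30 days of discharge related to the index surgery".
- **Research Question:** "Does application of PRP after CABG, cardiac surgery reduce the frequency of sternal wound complications".
- **Hypothesis:** "Administration of platelet rich plasma during sternal wound closure reduces the frequency of complications in the 30-days post-surgery period".
- **Objective:** a comparison of complication rates, in the plural.
- **Data Analysis:** "Categorical variables (superficial/deep wound infections, delayed healing, readmissions, transfusion requirements", followed by demographic variables. All are compared by chi-square or Fisher's exact test and judged at p<0.05.

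**The concern.** The Research Question and the Hypothesis ask whether PRP lowers the frequency of complications overall. The variable that would answer this, a per-patient indicator of any sternal wound complication, is neither defined nor listed for analysis. The variables that are listed are the components. They stand beside transfusion and demographic variables with nothing to mark which comparison decides the trial.

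An analyst who follows the document faithfully could report a significant component as the primary result, or a significant overall frequency as the primary result, and could make that choice after seeing the data. A reader of the final report could not tell from the protocol which result was meant to count.

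The readmission window adds to this. Counting from discharge and counting from surgery give different event sets, so a combined variable that includes readmission is undefined until one is chosen.

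**Working it through.** **1. The planned size.** Inputs from Sample size: 18% vs 44%, 5% significance, 80% power. The two-sided pooled-variance formula without continuity correction gives 49 per group, as stated, and power at 49 per group is 80.4%. The arithmetic is sound. The two rates are for oedema and infiltration, which is neither an overall complication frequency nor a listed component. The calculation therefore does not show which outcome is primary.

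**2. The passages side by side.**

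| Place | Form | Combining rule |
|---|---|---|
| Opening summary | several primary outcomes | none needed |
| Outcome; Operational Definitions item 3; Data Collection Procedure | one frequency made up of four items | none given |
| Research Question; Hypothesis | overall frequency | none given |
| Objective | complication rates | none given |
| Data Analysis | components only | overall variable not listed |

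**3. The readmission window.** Let D be the day of discharge counted from surgery. The definition counts events up to day D + 30. The outcome wording and the stated follow-up stop at day 30. For any D above 0, the defined window runs D days past the follow-up.

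**4. Can the choice change the conclusion?** The counts below are invented, at 49 per arm, PRP vs control, with two-sided p-values.

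*Example A.* Delayed healing in 2 vs 10 patients; another complication only in 7 vs 6. Any complication: 2 + 7 = 9 vs 10 + 6 = 16.
- Delayed healing: Fisher 0.028, chi-square 0.014.
- Any complication: Fisher 0.16, chi-square 0.105.

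*Example B.* No patient has two events. Any complication: 4 + 3 + 0 + 1 = 8 vs 8 + 6 + 1 + 3 = 18.
- Delayed healing 4 vs 8: chi-square 0.22.
- Superficial infection 3 vs 6: chi-square 0.29.
- Deep infection 0 vs 1: chi-square 0.31.
- Readmission 1 vs 3: chi-square 0.31.
- Fisher is larger for each of these.
- Any complication: Fisher 0.038, chi-square 0.022.

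In A only the component is significant; in B only the overall frequency is.

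**5. Error across four primary tests.** The nominal figure is 1 − 0.95⁴ = 18.5% (three tests: 1 − 0.95³ = 14.3%). At 49 per arm the true per-test error, e, differs from 5% because the tables are sparse. It was found by exact enumeration with equal rates in both arms. The four-test figure, assuming independence, is 1 − (1 − e)⁴.

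| Assumed rate per component | Fisher always | Fisher if an expected count <5, else chi-square | Uncorrected chi-square |
|---|---|---|---|
| 3% | 0.63% | 0.65% | 11.1% |
| 5% | 2.7% | 3.3% | 19.6% |
| 8% | 5.6% | 10.2% | 22.3% |

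At 8%, for example, e = 0.0143, 0.0266 and 0.0612, so the first entry is 1 − 0.9857⁴ = 5.6%. With complete overlap of the components, each four-test figure falls to the single-test e.

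The Introduction gives 0.4% to 8% for sternal complications, 0.2% to 8% for dehiscence and infection, and 0.4% to 3% for deep sternal wound problems. It gives no rate for delayed healing or readmission.

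**The case against.** The best defence is that the passages can be reconciled. They name essentially the same items, and the singular wording can be read as the frequency of each item in turn. The Objective's plural rates support that reading. So read, the opening summary, the Objective and the Data Analysis agree, and no overall variable has been left out. This stands to a degree. A reader might infer that the protocol sets out two incompatible primary endpoints, but the text does not go that far: it leaves open which of two is meant. The ambiguity remains, because the singular label, the Research Question and the Hypothesis equally allow the overall reading.

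A reader might also infer that the false-positive risk is 14.3% or 18.5%. The documents do not support that. At event rates of 3% to 5%, within the Introduction's ranges, Fisher or Fisher-when-sparse keeps the four-test error at 3.3% or below. Larger figures need uncorrected chi-square or higher rates. Higher rates cannot be excluded for delayed healing and readmission, for which no rate is given.

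The worked examples are constructed. Their control totals, 16/49 = 33% and 18/49 = 37%, are about four times the 8% upper figure in the Introduction, and Example B assumes no overlap between related events.

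It may be said that superficial and deep infection could be read as one variable or two. That is a thin point, since they are defined separately.

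Finally, the derivation of a composite, the choice between chi-square and Fisher, and the multiplicity method commonly belong to a SAP, which is not shown. That is fair, and none of these is counted against the protocol. Whether there is one primary outcome or several is a matter for the protocol itself.

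**Conclusion.** The point holds as an unresolved ambiguity. The protocol does not settle whether the primary outcome is one overall frequency or several outcomes. It gives no combining rule, its analysis list has no overall variable, and it marks no comparison as deciding. The discrepancy between the two readmission windows is real under either reading.

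The main harm is that the deciding result can be chosen after the data are seen. Examples A and B show that this can turn a positive trial into a negative one, or the reverse. They rest on invented counts and do not show how likely that is.

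Familywise inflation is secondary. For four independent tests it runs from about 0.6% to 22% over assumed rates of 3% to 8%, depending mostly on the test used, and it is lower if the components overlap. The planned 49 per group is arithmetically correct and is not in dispute.

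**What to change.** - State one primary endpoint, in the same words, in the opening summary, Outcome, Operational Definitions and Data Collection Procedure. An endpoint consistent with the Hypothesis would be the proportion of patients with at least one listed complication within 30 days of surgery, each patient counted once.
- Say whether readmission is part of it, and reconcile the readmission window with the follow-up.
- List that variable in the Data Analysis as the single deciding comparison at two-sided 0.05, with the components as supportive.
- If several primary outcomes are intended, say so in all of these places and control the error across them, for example by Holm.

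**Cost.** Wording in four places and one derived variable. No new data are needed if the 30-day post-surgery window is kept; a window running from discharge would need follow-up beyond day 30. With a single primary endpoint, no stand-alone claim can rest on one component. The 18% and 44% rates, given for oedema and infiltration, must be justified for the chosen endpoint, or the 80% power claim restated.

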Patients from 45 to 72 years of age, undergoing on pump CABG,

cardiac surgery with median sternotomy.

Patients who provide consent.

Exclusion criteria

- BMI less than **18.5** or more than **24.9**
- Bilateral harvesting of the internal mammary artery,
- Steroid therapy,
- Known Diabetic,
- Active smoker,
- Osteoporosis,
- Chronic lung disease,
- CPB time more than 72.5 minutes
- Platelet Rich Plasma cannot be obtained.
- Patients who are not candidates for blood bank donations.

Sample size

The sample size has been calculated by using WHO size calculator with the statistical assumptions as following:

(Level of significance = 5%), (Power of test = 80%), (Population standard deviation = 3.0)

(Anticipated population, rate of oedema and infiltration in prp group, P1= 18%)

Anticipated population, rate of oedema and infiltration in control group, P2= 44% Sample size comes out to be 49 cases in each study group and a total of 98 patients will be included in the study.

Sampling Technique

Participants will be recruited using non-probability consecutive sampling and randomly assigned to one of two groups.

Data Collection Procedure

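### One comparison is planned at 5%, but Data Analysis names no overall primary test and lets any of about nine outcomes, including undeclared hospital stay, be called significant at p<0.05

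*Protocol*

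**What the plan says.** The Hypothesis section makes one claim: "Administration of platelet rich plasma during sternal wound closure reduces the frequency of complications in the 30-days post-surgery period". The Sample size section plans one comparison ("Level of significance = 5%), (Power of test = 80" per cent) and arrives at 49 patients per arm.

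The outcomes are ranked. The primary outcome covers four components: superficial infection, deep infection (with mediastinitis), delayed healing and readmission. The opening summary refers to these as outcomes in the plural; the Outcome section and Data Collection Procedure use the singular. Cost is the secondary outcome. The third tier reads: "Other outcomes will be ICU stay (days), blood transfusions more than 4 units and platelets transfusions more than 4 units within 30 days".

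Data Analysis does not carry this ranking over. It lists variables by type, starting with "Quantitative variables (age, hospital stay, ICU stay, cost) will be summarized as mean", and assigns t-test or Mann-Whitney to the quantitative ones and chi-square or Fisher to the categorical ones. It then gives a single rule: "A p-value <0.05 will be considered significant". The infections, delayed healing, readmissions and transfusions stand as separate entries. No combined complication variable appears. Hospital stay is compared between arms, although the summary, the Outcome section, the operational definitions and Data Collection Procedure do not list it as an outcome. It occurs elsewhere only as a keyword.

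**The concern.** The 5% level in the sample size is attached to one comparison, while the analysis section gives the same 5% to each of about nine outcome tests and identifies none of them as the test of the hypothesis. Followed as written, the plan lets a report call PRP significantly beneficial on whichever outcome falls below 0.05. Because the four wound and readmission components are described in one place as primary outcomes, a chance result on any one of them could be presented as a primary result. Hospital stay adds a further test with no declared status. What is at stake is whether a reader of the final report can tell the planned test from a favourable result picked out of several.

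**Working it through.** **Inputs from the protocol.** Planning rates: "rate of oedema and infiltration in prp group, P1= 18" per cent and "rate of oedema and infiltration in control group, P2= 44" per cent; "Level of significance = 5" per cent; power 80%; 49 per arm.

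**1. The plan's own figure.** Pooled-variance formula for two proportions, two-sided, no continuity correction, with mean rate (0.18 + 0.44)/2 = 0.31:

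n = [1.96·√(2·0.31·0.69) + 0.8416·√(0.18·0.82 + 0.44·0.56)]² / 0.26² = (1.282 + 0.528)² / 0.0676 = 48.5, so 49 per arm.

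This matches. A one-sided test would give 39, so the planned level is a two-sided 5% for a single test.

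**2. Count of outcome tests in Data Analysis.**

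- Binary (6): superficial infection, deep infection, delayed healing, readmission, red cells above 4 units, platelets above 4 units.
- Quantitative (3): cost, ICU stay, hospital stay.

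The total is nine, or eight if the two transfusion items are merged. Age, residence, education and socioeconomic background are also compared, but they are not efficacy claims and are left out of the count.

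**3. Chance of at least one p<0.05 with no effect, independent tests each at exactly 5%.**

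- Nine outcomes: 1 − 0.95⁹ = 37.0%. Eight: 1 − 0.95⁸ = 33.7%.
- Nine, only in PRP's favour: 1 − 0.975⁹ = 20.4%.
- Three quantitative outcomes alone: 1 − 0.95³ = 14.3%.
- Four primary components alone: 1 − 0.95⁴ = 18.5%; in PRP's favour, 1 − 0.975⁴ = 9.6%.

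**4. Allowing for correlation.** Simulated normal test statistics with a common correlation (assumed; the protocol gives none), either direction:

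| Correlation | Nine outcomes | Four components |
|---|---|---|
| 0.3 | 32.6% | 17.4% |
| 0.5 | 27.0% | 15.7% |
| 0.8 | 16.6% | 11.3% |

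**5. Allowing for conservative tests of rare events.** Exact size at 49 per arm, using Fisher if there are fewer than 10 events in total and Pearson otherwise. This switching rule is an assumption, because the protocol does not say when each test applies. For four independent components with equal event rates, the chance is 1 − (1 − size)⁴:

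| Event rate (assumed) | Size per test | Any of four |
|---|---|---|
| 3% | 0.16% | 0.7% |
| 5% | 0.83% | 3.3% |
| 8% | 2.7% | 10.2% |
| 15% | 5.35% | 19.7% |
| 31% | 4.9% | 18.1% |

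The choice of test matters as much as the rate. At 5% events, Fisher throughout gives 2.7% and Pearson throughout about 20%.

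For all nine outcomes, with the six binary ones at 5% events: 1 − (1 − 0.0083)⁶ × 0.95³ ≈ 18.5%. At 15% events the same formula gives about 38%, slightly above 37% because Pearson's test runs a little over 5% there.

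**The case against.** The strongest reply has four parts.

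*The outcomes are already ranked, and unadjusted 5% tests of secondary outcomes are common practice.* The ranking is real. A reader might infer that the trial carries a 37% false-positive rate. The documents do not support that. Nowhere does the protocol say that success on any one of nine outcomes proves efficacy, 37% assumes independence, and it counts results against PRP as well as for it. What remains is that Data Analysis drops the ranking and names no test for the top tier.

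*A statistical analysis plan not shown may deal with multiplicity.* This also stands, so the absence of an adjustment method is not the point. The point rests on what the protocol does fix: one threshold for every listed variable, with no overall primary test among them.

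*Inflation among the four primary components is not established.* This is correct at low event rates. The Introduction cites wound complications in 0.2% to 8% of patients and deep problems in 0.4% to 3% of unselected patients, and the exclusion criteria remove several risk groups. With Fisher's test for rare events, the four-component figure can fall below 5%. The protocol gives no rate for delayed healing or readmission, and higher rates there would raise it. So a general claim that the primary family is inflated cannot be made from the documents.

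*The baseline comparisons are a matter of reporting style.* This is accepted. One might add them to reach 13 tests and 48.7%, but they are not claims about PRP. The protocol describes no adjusted analysis that they would feed.

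**Conclusion.** The point holds in a limited form. The protocol plans one two-sided 5% comparison for one hypothesis, but its analysis section contains no test of that hypothesis as a whole and gives the word significant to any of about nine outcomes, one of them undeclared. Under no effect, every nine-outcome scenario above puts the chance of at least one p<0.05 at roughly 17% to 38%, well above 5%. In the rare-event case this is largely because the three quantitative tests alone contribute 14.3% if independent. In PRP's favour only, the independent figure is about 20%. These values rest on assumed correlations, event rates and test choice. For the four primary components the range is wide, about 3% at 5% event rates to about 20% at 15%, and the protocol does not settle where the trial lies. The inconsistency over hospital stay needs no assumption. The change should be made before the data are analysed; nothing here invalidates the design.

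**What to change.** In Data Analysis, state that the primary analysis is one two-sided 5% test comparing, between arms, the proportion of patients with at least one of the listed primary complications within 30 days. Reserving significance for the primary outcome without naming this single variable would achieve nothing, since only components are now tested. The variable also needs one time window: the primary outcome counts 30 days from surgery, whereas the definition of readmission counts from discharge.

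Report the individual components and all secondary and other outcomes as between-arm differences with 95% confidence intervals, labelled supportive, with no claim of significance. Add hospital stay to the other outcomes or delete it from Data Analysis. Optionally, tabulate baseline variables by arm without p-values.

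The cost is wording, and fewer variables may be called significant. A single 5% test keeps 49 per arm at the protocol's own planning rates. Those rates are for oedema and infiltration, so they do not show that the combined variable has the planned power. Splitting the level instead would be expensive at the same rates: Bonferroni over four components (0.05/4 = 0.0125) needs 70 per arm, with 61.7% power at 49. Over nine outcomes (0.05/9 = 0.0056) it needs 82 per arm, with 50.4% power at 49.
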